7.2 Other safety evaluations

7.2.1 Sheehan suicidality tracking scale score (S-STs)

Sheehan suicidality tracking scale (S-STs) is a fourteen-item (up to 22) scale. Each item in the S-STs is scored on a 5-point Likert scale (0=not at all, 1= a little, 2=moderately, 3=very, and 4=extremely). Data from the S-STs will be analyzed as individual item scores, suicidal ideation subscale score (sum of scores from items 2, 3 and 4, plus score from item 5 if ≤ 1), suicidal behavior subscale score (sum of scores from items 6, 7a and 8, plus score from item 5 if > 1). Items and scores (including the 2 subscales and the total score) data will be listed by treatment, subject and visit/time; abnormalities will be flagged.

7.2.1.1 Descriptive analyses

Commercially Confidential Information

7.2.2 Clinical-Administered Dissociative States Scale (CADSS)

7.2.2.1 Descriptive analyses

CADSS total score data will be listed by treatment, subject and visit/time; abnormalities will be flagged.

Commercially Confidential Information

7.2.2.2 Statistical model, assumptions and hypotheses

The total CADSS score will be also modeled with interest at 6 weeks, using MMRM with fixed, categorical effects of treatment, time (at all planned timepoints), and treatment*time interaction.

Commercially Confidential Information

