
 
To assess risk of mania induction.
 
To assess efficacy in the melancholic subtype of depression.
 
To assess safety and tolerability, especially dissociative side effects.
 
To assess most effective dose and dosing regimen.
 
To assess MIJ821 pharmacokinetics in plasma.
 
To assess impact of MIJ821 on suicidality.
 
To assess efficacy of MIJ821 on measures of response and remission
 
To assess efficacy of MIJ821 for mixed mood symptoms.
 
To assess efficacy of MIJ821 for anxiety symptoms.
 
	
 
Young Mania Rating Scale at 24 hours, 48 hours (if applicable) and 6 weeks post-dose.
 
Bech-Rafaelsen Melancholia and CORE scale change from baseline to 24 hours, 48 hours (if applicable) and 6 weeks post-dose.
 
Incidence of adverse event Dissociative rating scales (Clinician-Administered Dissociative States Scale, and Dissociative Experiences Scale) change from baseline to 24 hours, 48 hours (if applicable) and 6 weeks post-dose.
 
Montgomery Asberg Depression Rating Scale score at 6 weeks.
 
PK properties of MIJ821 in plasma described by AUClast, AUC0-24h, Cmax, Tmax (parameters not limited)
 
Sheehan Suicidality Tracking Scale changes from baseline at 24 hours, 48 hours (if applicable), and 6 weeks after the start of first infusion.
 
% treatment response (>50% improvement in MADRS) at 24 hours, 48 hours (if applicable), and 6 weeks after the start of first infusion. % treatment remission (MADRS<7) at 24 hours, 48 hours (if applicable), and 6 weeks after the start of first infusion CGI-S and CGI-I scores at 24 hours, 48 hours (if applicable), and 6 weeks after the start of first infusion
 
Koukopoulos Mixed Depression Rating Scale change from baseline to 24 hours, 48 hours, and 6 weeks after the start of first infusion.
 
Hamilton Anxiety Scale change from baseline to 24 hours, 48 hours (if applicable), and 6 weeks after the start of first infusion
 

Objective(s)	Endpoint(s)

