### **3 Study design**

This is a non-confirmatory, multi-center, 6-treatment arm in the European countries and 5-treatment arm in the USA (no ketamine arm), randomized, subject and investigator blinded, parallel group, placebo controlled study in treatment-resistant depression patients. The study will randomize approximately 66 Subjects and while the study design utilizes an outpatient visit schedule, the study allows for the inclusion of subjects seeking treatment for their disease from both an 'inpatient' or 'outpatient' clinic setting.

A screening period of maximum 4 weeks will be used to assess eligibility. Patients who meet the eligibility criteria at screening will proceed to baseline evaluations on Day-1 or Day 1. All baseline safety evaluation results must be available prior to randomization. At the baseline visit, eligible subjects will be randomized to one of the treatment arms. Randomized subjects will enter a 36- day treatment period, receiving at each treatment visit, a 40-minute infusion with a safety observation period of 2-4 hours (i.e. a minimum of 2 hours) post the start of

infusion. If the subject reports no dissociative symptoms and no suicidal symptoms, the subject will be allowed to leave the clinical treatment setting. Visits to assess efficacy and safety are scheduled at 24 hours, 48 hours (if applicable) and every week during the treatment period. If 48 hour visit (V103) is conducted, then all assessments should be completed. The assessment to address the primary objective will be performed at 24 hour post-dose. Safety assessments will include physical examinations, ECGs, vital signs, standard clinical laboratory evaluations (hematology, blood chemistry, and urinalysis), adverse event and serious adverse event monitoring. At the conclusion of the treatment period (Day 1 - Day 36), subjects will enter a 5-week follow up period consisting of two follow visits approximately 1 week (Day 43) and 3 weeks (Day 57) after the last study drug administration and an end of study completion visit (Day 71) The total duration for each subject in the study is maximum 14-weeks including screening and baseline. No interim analysis is planned. The study design is summarized in [Figure 3-1](#) below for the European countries (same study design without the ketamine arm in the USA).

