### **4.3 Rationale for choice of control drugs (comparator/placebo) or combination drugs**

The use of placebo saline solution is to provide a comparison group for an unbiased collection and assessment of safety and tolerability data.

Ketamine is included primarily for assay sensitivity and for comparison of side effects. Ketamine is known to be effective with large effect sizes for severe depressive episodes, and it also has high rates of dissociative side effects in 20-30% of subjects, often of moderate to marked severity. It also can cause manic episodes, mixed states, and suicidal or aggressive reactions in a small minority of persons. A single subanesthetic dose of intravenous ketamine consistently decreases symptoms of depression in subjects with treatment-resistant depression in a rapid (within hours), robust (across many symptoms of depression) and relatively sustained (typically, 7–14 days) manner ([Berman et al 2000](#); [Cusin et al 2017](#)). Repeated doses (six infusions over the course of several weeks) have shown promise from an efficacy and safety standpoint ([Aan het Rot et al 2010](#)). The efficacy of two times versus three times a week intravenous ketamine in subjects with treatment-resistant depression in sustaining the initial antidepressant effects was evaluated. Both doses (0.5 and 0.75 mg/kg) were significantly superior to placebo in treating depression symptoms and the transient dissociative side effects attenuated with repeat dosing ([Singh et al 2016](#)). One study examined the benefits of a fixed course of 4 once-weekly ketamine sessions (0.5 mg/kg IV) as continuation phase treatment in 5 patients who had remitted after acute phase treatment. All 5 patients maintained improvement during the continuation phase ([Krystal et al 1994](#)).

To limit any dissociative and psychomimetic side effects, the limiting dose for Ketamine infusion is at 40 mg/infusion for patients over 80 kg.

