Benefits of ketamine have been shown for rapid improvement of depressive symptoms within 1-2 days, which persists up to 3-4 weeks after one dose. This improvement has been shown mainly with intravenous infusion of 0.5 mg/kg ketamine over 40 minutes ([Katalinic et al 2013](#)). Two open-studies ([Price et al 2009](#), [Thakurta et al 2012](#)) also have suggested that ketamine may be an appropriate treatment to rapidly reduce acute suicide risk in depressed patients. Benefits have been shown also recently with intranasal administration of esketamine. These benefits occur for acute depressive symptoms, and have not been studied or proven for long-term or maintenance administration. The amount of benefit seen acutely meets or exceeds the effect sizes seen with standard antidepressants. Some studies report such benefit in treatment-resistant depression, with patients who have failed multiple prior antidepressant trials. Such benefit has been seen with both bipolar and unipolar depression.

Most of the research conducted using subanaesthetic doses of ketamine has shown psychotomimetic and neuropsychological adverse effects: general psychiatric symptoms, agitation, dissociative symptoms and manic symptoms. These effects have mostly been restricted to the time of administration, disappearing completely by 60 minutes afterward. Other adverse events experienced by patients include feelings of intoxication and lowered inhibitions, confusions, decreased concentration and perceptual disturbances. Most of these

impairments were only apparent during the infusions, and none persisted longer than 2 hours after the beginning of the infusions.

There have been not many significant physical adverse event reported in studies of low-dose ketamine (used as an antidepressant) to date. Some studies have reported a variety of non-permanent physical effects such as light-headedness, headache, nausea, diplopia, drowsiness and dizziness. These symptoms tend to be benign and again limited to the period of the infusion or for a short time following.

Depression trials investigating subanaesthetic doses of ketamine consistently report transient elevations in blood pressure and heart rate during the period of infusion and for up to 80 minutes after dosing.

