Clinical Global Impression of Improvement							X	X	X		X		X		X			X		X	X	X	

Epoch	Screening		Treatment																Follow up		End of Study	
Visit Name	Screening	Baseline	Treatment																201	202	299	
Visit Numbers 	1	2	101				102	103 	104		105		106		107			108		201	202	299
Days	-28 to -2	-1 to 1	1				2	3	8		15		22		29			36		43	57	71
Time (post-dose)	-	-	0h 	CCI	1h	4h	24h	48h	0h 	2-4h	0h 	2-4h	0h 	2-4h	0h 	0.67h 	2-4h	0h 	2-4h	-	-	-
Clinician Administered Dissociative States Scale		X	X 		X		X	X	X		X		X		X			X		X	X	X
Dissociative Experiences Scale (DES)		X	X 		X	X	X	X	X		X		X		X			X		X	X	X
Generic Assessment of Side Effects in Clinical Trials (patient self-rating)		X	X 		X		X	X	X		X		X		X			X		X	X	X
Hamilton Anxiety Rating Scale		X											X							X		
Koukopoulos Mixed Depression Rating Scale		X	X 		X		X	X	X		X		X		X			X		X	X	X
Sheehan Suicidality Scale	X	X	X 		X		X	X	X		X		X		X			X		X	X	X
Adverse Events	X	X	X 	X	X		X	X	X		X		X		X			X		X	X	X
Serious Adverse Events	X	X	X 	X	X		X	X	X		X		X		X			X		X	X	X

Epoch	Screening		Treatment																Follow up		End of Study	
Visit Name	Screening	Baseline	Treatment																Follow up		End of Study	
Visit Numbers 	1	2	101				102	103 	104		105		106		107		108		201	202	299	
Days	-28 to -2	-1 to 1	1				2	3	8		15		22		29		36		43	57	71	
Time (post-dose)	-	-	0h 	CCI	1h	4h	24h	48h	0h 	2-4h	0h 	2-4h	0h 	2-4h	0h 	0.67h 	2-4h	0h 	2-4h	-	-	-

Commercially Confidential Information

Study completion information																					X		
Comments	X	X	X	X			X	X	X		X		X		X				X	X	X	X	

X Assessment to be recorded in the clinical database or received electronically from a vendor

 Visit structure given for internal programming purpose only

 Unless specified in the Assessment Schedule, all assessments are to be done before start of infusion

Commercially Confidential Information

 S = assessment to be recorded on source documentation only and will not be entered into the eCRF. If drug screen result is positive but does not meet DSM-5 criteria for substance use disorder, the subject can be enrolled.

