 Additional pregnancy testing may be performed at each visit to meet local requirements.

 Serum pregnancy test

 Urine pregnancy test

 Not to be repeated if baseline visit and V101 are conducted on the same day.

Commercially Confidential Information

 24 hours after start of the first infusion

 V103 48 hours is an optional visit, however if V103 is conducted, all assessments should be completed.

 Assessments to be conducted once between 2 and 4 hours, and at 6 hours if there is an extended stay.

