1.3.2. Secondary objective(s)

Secondary objective(s)	Endpoints related to secondary objectives

 To assess risk of mania induction 	
 Young Mania Rating Scale at 24 hours, 48 hours (if applicable) and 6 weeks post-dose.

 To assess efficacy in the melancholic subtype of depression. 	
 Bech-Rafaelsen Melancholia and CORE scale change from baseline to 24 hours, 48 hours (if applicable) and 6 weeks post-dose.

 To assess safety and tolerability, especially dissociative side effects. 	
 Incidence of adverse event Dissociative rating scales (Clinician-Administered Dissociative States Scale, and Dissociative Experiences Scale) change from baseline to 24 hours, 48 hours (if applicable) and 6 weeks post-dose.

 To assess most effective dose and dosing regimen. 	
 Montgomery Åsberg Depression Rating Scale score at 6 weeks.

 To assess MIJ821 pharmacokinetics in plasma 	
 PK properties of MIJ821 in plasma described by AUClast, AUC0-24h,

	Cmax, Tmax (parameters not limited)

 To assess impact of MIJ821 on suicidality 	
 Sheehan Suicidality Tracking Scale changes from baseline at 24 hours, 48 hours (if applicable), and 6 weeks after the start of first infusion.

 To assess efficacy of MIJ821 on measures of response and remission 	
 % treatment response (>50% improvement in MADRS) at 24 hours, 48 hours (if applicable), and 6 weeks after the start of first infusion. % treatment remission (MADRS<7) at 24 hours, 48 hours (if applicable), and 6 weeks after the start of first infusion CGI-S and CGI-I scores at 24 hours, 48 hours (if applicable), and 6 weeks after the start of first infusion

 To assess efficacy of MIJ821 for mixed mood symptoms. 	
 Koukopoulos Mixed Depression Rating scale change from baseline to 24 hours, 48 hours (if applicable), and 6 weeks after the start of first infusion.

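### The SAP's onset/resolution table for adverse events of interest omits ketamine, and the readable text names CADSS only at times well after the acute effect the protocol describes

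*SAP*

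**What the plan says.** Protocol Table 2-1 and SAP 1.3.2 share a secondary objective: "To assess safety and tolerability, especially dissociative side effects". The matching endpoint in Table 2-1 reads "Incidence of adverse event Dissociative rating scales (Clinician-Administered Dissociative States Scale, and Dissociative Experiences Scale) change from baseline to 24 hours, 48 hours", followed by 6 weeks; SAP 1.3.2 gives the same times. The 48 h visit (V103) is optional.

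On the CADSS model, SAP 7.2.2.2 states "The total CADSS score will be also modeled with interest at 6 weeks", using a mixed model for repeated measures with treatment, time at all planned timepoints, and their interaction. SAP 7.2.2.1 lists CADSS by treatment, subject and visit/time. The rest of both sections is redacted.

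Protocol 4.3 gives the role of the active comparator: "Ketamine is included primarily for assay sensitivity and for comparison of side effects". There is no ketamine arm in the USA (Protocol 5), and randomisation is stratified by region (Protocol 6.3.2).

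SAP 7.1.1 defines a summary of frequency, time to onset and time to resolution for dissociation, amnesia, the two together, sedation and vomiting. Its columns are two pooled MIJ821 dose groups, placebo, and a total. The similar table in SAP 2 (first interpretable results) is described only as by treatment.

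**The concern.** There are two separate gaps.

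First, the onset/resolution table is where a reader would compare how soon dissociation starts and how long it lasts. The arm included for side-effect comparison is not among its columns, and the SAP does not say whether the total includes that arm. If it does, the total mixes ketamine events into a figure shown beside MIJ821 and placebo. If it does not, ketamine is absent from the table.

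Second, on the protocol's own account, ketamine's dissociative effects have gone before any of the named CADSS times. Similar scores across arms at 24 h, 48 h or 6 weeks would then say little about acute dissociation, but could be read as comparable dissociative tolerability. The one rating taken at a suitable moment has no stated status in readable text. Its prominence could therefore be decided after the results are known.

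**Working it through.** The documents give no figure to reproduce. The check compares times and columns.

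**Inputs**
- Infusion length (Protocol 3): "receiving at each treatment visit, a 40-minute infusion".
- Duration of ketamine's psychotomimetic effects, dissociative symptoms included (Protocol 4.5): "These effects have mostly been restricted to the time of administration, disappearing completely by 60 minutes afterward". The same section adds that most impairments were seen only during the infusion and that none lasted more than 2 h from its start.
- CADSS collection times: the CADSS row of Protocol Table 8-1.
- Timing rule (Table 8-1, footnote 2): "Unless specified in the Assessment Schedule, all assessments are to be done before start of infusion".

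**Step 1: the window.** The first statement gives 40 + 60 = 100 min, and 100/60 = 1.67 h from infusion start. The second gives 2 h directly. I use 2 h, the longer of the two.

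**Step 2: the clock.** Footnote 11 defines a time as "24 hours after start of the first infusion". The Day 29 column at 0.67 h (0.67 × 60 = 40 min) matches the end of infusion. Both suggest that post-dose time runs from infusion start. The 1 h rating is then 60 − 40 = 20 min after the infusion ends. If 1 h were counted from infusion end, it would fall at 40 + 60 = 100 min = 1.67 h from the start, still inside 2 h.

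**Step 3: CADSS ratings after the first infusion starts**

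| Rating | Named endpoint time? | Relation to the 2 h window |
|---|---|---|
| Day 1, 1 h | No | Inside |
| 24 h | Yes | 24 − 2 = 22 h past it |
| 48 h (optional) | Yes | 48 − 2 = 46 h past it |
| Days 8, 15, 22, 29, 36 (0h column) | Only if 6 weeks means Day 36 | Before that day's infusion |
| Day 43 | Yes, if 6 weeks runs from Day 1 (1 + 42 = 43) | 43 − 36 = 7 days after the last infusion visit |
| Days 57, 71 | No | Later still |

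The count is 3 + 5 + 3 = 11, or 10 if V103 is not held, and one rating is inside the window. If 6 weeks is read as Day 36 before infusion, the gap is still 36 − 29 = 7 days from the previous infusion visit. With the 1.67 h reading, the first two gaps become 22.3 h and 46.3 h, which changes nothing. No CADSS rating is scheduled at Day 1 4 h or in any 2-4 h column.

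**Step 4: where ketamine adverse events appear**

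| Output | Ketamine shown? |
|---|---|
| Psychotomimetic event incidence, Protocol 12.5.2 | Yes, by treatment group |
| General event tables, SAP 7.1.1 | Yes, by treatment |
| Onset and resolution listings, SAP 7.1.1 interim paragraph | Yes, by treatment group and subject |
| Onset/resolution summary table, SAP 7.1.1 | No column; content of the total not stated |
| Similar table, SAP 2 | Not specified beyond by treatment |

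No interval width can be given, because the allocation is redacted and readable text gives no CADSS variance.

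**The case against.** The strongest reply is that the CADSS part rests on silence next to redactions. The sentence on the 6-week interest is followed at once by blacked-out text, and most of the CADSS descriptive section is hidden. The planned model already carries the 1 h rating through its treatment-by-time term. Protocol 8.3.4 calls the secondary-scale results descriptive and hypothesis-generating, and a 6-week focus makes sense for repeated infusions. Acute dissociation is also covered elsewhere: by the 2-4 h observation after each infusion starts, by adverse-event tables by arm, and by DES ratings at 1 h and 4 h on Day 1.

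Much of this stands, and it rules out three stronger readings that a reader might infer:
- *The 1 h rating goes unanalysed.* It does not: it is in the model and the listings, and hidden text may summarise it.
- *The plan has no ketamine side-effect comparison.* It has incidence by treatment group and onset/resolution listings. Only the one summary table lacks the arm.
- *The named times are wrong.* They remain useful for persistent or cumulative effects. The stated time course is for ketamine; readable text gives none for MIJ821.

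The reply does not remove two things. The column list in SAP 7.1.1 is not redacted, and it omits ketamine. The endpoint tables are also readable, and name no acute CADSS time. DES does not fill that place, because it asks about experiences in daily life.

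**Conclusion.** The point holds as a low-cost improvement. The missing ketamine column is the firmer half, since it does not depend on redacted text and sits poorly with the stated purpose of that arm. The CADSS half is a matter of naming. All named times fall at least 22 h after the roughly 2 h in which the protocol places ketamine's effects, and the only rating inside that window, 1 of 11 (or 1 of 10), is not a stated time of interest in readable text.

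This assumes that post-dose time runs from infusion start (the conclusion survives the alternative), that the protocol's account of ketamine applies here, and that redacted text does not already name the 1 h contrast. If it does, only the alignment of the endpoint tables remains of the CADSS half. The primary analysis is not affected.

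**What to change.** Make the change in the SAP only.

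1. **SAP 7.1.1.** Add a ketamine column to the onset/resolution table, footnoted as European subjects only. State whether the total includes ketamine. Describe the SAP 2 table in the same way.
2. **SAP 1.3.2 and 7.2.2.2, unless redacted text already does this.** Name the Day 1 1 h CADSS contrast as the acute tolerability estimate, with a 95% CI, for MIJ821 versus placebo and MIJ821 versus ketamine. Restrict the ketamine contrast to European subjects or account for region, because US subjects could not be randomised to ketamine. Keep 24 h, 48 h and 6 weeks, labelled as persistence estimates.
3. **Estimation.** Use a mixed model with time-specific variances, or a separate analysis of the 1 h score. Scores soon after an infusion may be far more variable than pre-infusion scores, so a common variance could give a misleading 1 h interval. The readable text does not state the covariance structure.

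Protocol Table 2-1 should be aligned at the next amendment made for other reasons. Protocol 14.1 requires a written, approved amendment for any change, and this wording alone does not warrant one. Until then, the SAP should mark the 1 h contrast as its own addition. No change is asked for DES.

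The cost is SAP wording and one table column, with no new data, visit or procedure. The downside is one more descriptive secondary contrast, likely with a wide interval given about 66 subjects over six arms. The ketamine comparison loses the US subjects if restricted to Europe.

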7.2.3 Dissociative Experiences Scale (DES)

7.2.3.1 Descriptive analyses

Commercially Confidential Information

7.2.3.2 Statistical model, assumptions and hypotheses

Commercially Confidential Information

7.2.3.2.1 Supportive analysis

Commercially Confidential Information

7.3 Graphical presentation

Commercially Confidential Information

Commercially Confidential Information

Commercially Confidential Information
